13.1 Regulatory and ethical compliance

This clinical study was designed and shall be implemented, executed and reported in accordance with the ICH Harmonized Tripartite Guidelines for Good Clinical Practice, with applicable local regulations (including European Directive 2001/20/EC, US CFR 21), and with the ethical principles laid down in the Declaration of Helsinki.

13.2 Responsibilities of the investigator and IRB/IEC

Before initiating a trial, the investigator/institution must obtain approval/favorable opinion from the Institutional Review Board/Independent Ethics Committee (IRB/IEC) for the trial protocol, written informed consent form, consent form updates, patient recruitment procedures (e.g., advertisements) and any other written information to be provided to patients. Prior to study start, the investigator is required to sign a protocol signature page confirming his/her agreement to conduct the study in accordance with these documents and all of the instructions and procedures found in this protocol and to give access to all relevant data and records to Novartis monitors, auditors, Novartis Quality Assurance representatives, designated agents of Novartis, IRBs/IECs, and regulatory authorities as required. If an inspection of the clinical site is requested by a regulatory authority, the investigator must inform Novartis immediately that this request has been made.

13.3 Publication of study protocol and results

The protocol will be registered in a publicly accessible database such as clinicaltrials.gov and as required in EudraCT. In addition, after study completion (*e.g.*, *defined as last patient last visit*) and finalization of the study report the results of this trial will be submitted for publication and posted in a publicly accessible database of clinical trial results, such as the Novartis clinical trial results website and all required Health Authority websites (e.g. Clinicaltrials.gov, EudraCT etc.).

For details on the Novartis publication policy including authorship criteria, please refer to the Novartis publication policy training materials that were provided to you at the trial investigator meetings.

13.4 Quality Control and Quality Assurance

Novartis maintains a robust Quality Management System (QMS) that includes all activities involved in quality assurance and quality control, to ensure compliance with written Standard Operating Procedures as well as applicable global/local GCP regulations and ICH Guidelines.

Audits of investigator sites, vendors, and Novartis systems are performed by auditors, independent from those involved in conducting, monitoring or performing quality control of the clinical trial. The clinical audit process uses a knowledge/risk based approach.

Audits are conducted to assess GCP compliance with global and local regulatory requirements, protocols and internal SOPs, and are performed according to written Novartis processes.

14 Protocol adherence

This protocol defines the study objectives, the study procedures and the data to be collected on study participants. Additional assessments required to ensure safety of patients should be administered as deemed necessary on a case by case basis. Under no circumstances including incidental collection is an investigator allowed to collect additional data or conduct any additional procedures for any purpose involving any investigational drugs under the protocol, other than the purpose of the study. If despite this interdiction prohibition, data, information, observation would be incidentally collected, the investigator shall immediately disclose it to Novartis and not use it for any purpose other than the study, except for the appropriate monitoring on study participants.

Investigators ascertain they will apply due diligence to avoid protocol deviations. If an investigator feels a protocol deviation would improve the conduct of the study this must be considered a protocol amendment, and unless such an amendment is agreed upon by Novartis and approved by the IRB/IEC and health authorities, where required, it cannot be implemented.

16.1 Appendix 1: Vital signs

Notable Vital Signs and Body Weight

Vital Sign Variable Notable Criteria

Pulse (beats/min) >120 bpm

Or

< 55 bpm

Systolic BP (mmHg) $\geq 160 \text{ mmHg}$

Or

≤ 90 mm Hg

Diastolic BP (mmHg) ≥ 100 mmHg or

 $\leq 50 \text{ mmHg}$

Temperature (°C) >38.3 °C/101°F

Body weight (kg) \pm 7% from baseline weight

16.2 Appendix 2: Liver event definition and follow up requirements

Table 16-1 Liver Event and Laboratory Trigger Definitions

	Definition/threshold
LIVER LABORATORY	• 3 x ULN < ALT / AST ≤ 5 x ULN
TRIGGERS	• 1.5 x ULN < TBL ≤ 2 x ULN
LIVER EVENTS	ALT or AST > 5 × ULN
	 ALP > 2 × ULN (in the absence of known bone pathology)
	 TBL > 2 × ULN (in the absence of known Gilbert syndrome)
	ALT or AST > 3 × ULN and INR > 1.5
	 Potential Hy's Law cases (defined as ALT or AST > 3 × ULN and TBL > 2 × ULN (mainly conjugated fraction) without notable increase in ALP to > 2 × ULN)
	Any clinical event of jaundice (or equivalent term)
	 ALT or AST > 3 × ULN accompanied by (general) malaise, fatigue, abdominal pain, nausea, or vomiting, or rash with eosinophilia
	Any adverse event potentially indicative of a liver toxicity*

^{*}These events cover the following: hepatic failure, fibrosis and cirrhosis, and other liver damagerelated conditions; the non-infectious hepatitis; the benign, malignant and unspecified liver neoplasms TBL: total bilirubin; ULN: upper limit of normal

Table 16-2 Follow Up Requirements for Liver Events and Laboratory Triggers

Criteria	Actions required	Follow-up monitoring
Potential Hy's Law caseª	 Discontinue the study treatment immediately Hospitalize, if clinically appropriate Establish causality Record the AE and contributing factors (e.g., conmeds, med hx, lab) in the appropriate eCRF 	ALT, AST, TBL, Alb, PT/INR, ALP and GGT until resolution ^c (frequency at investigator discretion)
ALT or AST		
> 8 × ULN	 Discontinue the study treatment immediately Hospitalize if clinically appropriate Establish causality Record the AE and contributing factors (e.g., conmeds, med hx, lab) in the appropriate eCRF 	ALT, AST, TBL, Alb, PT/INR, ALP and GGT until resolution ^c (frequency at investigator discretion)
> 3 × ULN and INR > 1.5	 Discontinue the study treatment immediately Hospitalize, if clinically appropriate Establish causality 	ALT, AST, TBL, Alb, PT/INR, ALP and GGT until resolution ^c (frequency at investigator discretion)

Criteria	Actions required	Follow-up monitoring
	• Record the AE and contributing factors (e.g., conmeds, med hx, lab) in the appropriate eCRF	
	• Repeat LFT within 48 hours	
> 5 to ≤ 8 × ULN	• If elevation persists, continue follow-up monitoring	
	 If elevation persists for more than 2 weeks, discontinue the study drug Establish causality 	ALT, AST, TBL, Alb, PT/INR, ALF and GGT until resolution ^c (frequency at investigator discretion)
	 Record the AE and contributing factors (e.g., conmeds, med hx, lab) in the appropriate eCRF 	,
	Discontinue the study treatment immediately	
> 3 × ULN accompanied by symptoms ^b	 Hospitalize if clinically appropriate 	ALT, AST, TBL, Alb, PT/INR, AL and GGT until resolution ^c
	 Establish causality 	(frequency at investigator
	 Record the AE and contributing factors (e.g., conmeds, med hx, lab) in the appropriate eCRF 	discretion)
> 2 to < E v III N (notion)	• Repeat LFT within the next week	Investigator discretion Monitor LFT within 1 to 4 weeks
> 3 to ≤ 5 × ULN (patient is asymptomatic)	 If elevation is confirmed, initiate close observation of the patient 	
ALP (isolated)		
, ,	 Repeat LFT within 48 hours 	
> 2 × ULN (in the absence of known bone pathology)	• If elevation persists, establish causality	Investigator discretion Monitor LFT within 1 to 4 weeks
	• Record the AE and contributing factors (e.g., conmeds, med hx, lab) in the appropriate eCRF	or at next visit
TBL (isolated)		
,	• Repeat LFT within 48 hours	
> 2 × ULN (in the absence of known Gilbert syndrome)	• If elevation persists, discontinue the study drug immediately	ALT, AST, TBL, Alb, PT/INR, ALF and GGT until resolution ^c
	 Hospitalize if clinically appropriate 	(frequency at investigator discretion)
	• Establish causality	Test for hemolysis (e.g.,
	 Record the AE and contributing factors (e.g., conmeds, med hx, lab) in the appropriate eCRF 	reticulocytes, haptoglobin, unconjugated (indirect) bilirubin)
	• Repeat LFT within the next week	Investigator discretion
> 1.5 to ≤ 2 × ULN (patient is asymptomatic)	• If elevation is confirmed, initiate close observation of the patient	Monitor LFT within 1 to 4 weeks or at next visit

Criteria	Actions required	Follow-up monitoring
Jaundice	 Discontinue the study treatment immediately 	
	• Hospitalize the patient	ALT, AST, TBL, Alb, PT/INR, ALP and GGT until resolution ^c (frequency at investigator discretion)
	• Establish causality	
	 Record the AE and contributing factors (e.g., conmeds, med hx, lab) in the appropriate eCRF 	
	 Consider study treatment interruption or discontinuation 	
Any AE potentially indicative of a liver toxicity*	 Hospitalization if clinically appropriate 	Investigator discretion
	 Establish causality 	Investigator discretion
	 Record the AE and contributing factors (e.g., conmeds, med hx, lab) in the appropriate eCRF 	

^aElevated ALT/AST > 3 × ULN and TBL > 2 × ULN but without notable increase in ALP to > 2 × ULN b (General) malaise, fatigue, abdominal pain, nausea, or vomiting, or rash with eosinophilia c Resolution is defined as an outcome of one of the following: (1) return to baseline values, (2) stable values at three subsequent monitoring visits at least 2 weeks apart, (3) remain at elevated level after a maximum of 6 months, (4) liver transplantation, and (5) death.

Based on investigator's discretion investigation(s) for contributing factors for the liver event can include: serology tests, imaging and pathology assessments, hepatologist's consultancy; obtaining more detailed history of symptoms and prior or concurrent diseases, history of concomitant drug use, exclusion of underlying liver disease.

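### If 'isolated', which is undefined, has its ordinary meaning, Table 16-2 mandates a weaker stopping action for a combined ALT/AST, ALP and bilirubin rise than for bilirubin alone

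*Protocol*

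**What the plan says.** All of this is in Protocol section 16.2 (Appendix 2) unless stated.

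- **Table 16-1, bilirubin.** One listed liver event is "TBL > 2 × ULN (in the absence of known Gilbert syndrome". It carries no condition on ALT, AST or ALP.
- **Table 16-1, Hy's Law.** "Potential Hy's Law cases (defined as ALT or AST > 3 × ULN and TBL > 2 × ULN (mainly conjugated fraction"; the definition goes on to require that this be "without notable increase in ALP to > 2 × ULN". Footnote a to Table 16-2, attached to the Hy's Law action row, has the same thresholds but no condition on the conjugated fraction.
- **Table 16-2, TBL (isolated), above 2×ULN.** Repeat liver tests within 48 hours, then: "If elevation persists, discontinue the study drug immediately".
- **Table 16-2, ALT/AST above 5 and up to 8×ULN.** Repeat within 48 hours, keep monitoring, and: "If elevation persists for more than 2 weeks, discontinue the study drug".
- **Table 16-2, ALT/AST above 3 and up to 5×ULN, asymptomatic.** Repeat within a week, then: "If elevation is confirmed, initiate close observation of the patient". No stop is mandated.
- **Table 16-2, immediate-stop rows.** Potential Hy's Law, ALT/AST above 8×ULN, "> 3 × ULN and INR > 1.5", "> 3 × ULN accompanied by symptoms", and jaundice.
- **Table 16-2, ALP (isolated), above 2×ULN.** Repeat and assess causality. No stop is mandated.
- **Table 16-2, adverse events that may indicate liver toxicity.** Interruption or discontinuation is to be considered.

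Section 9.1.1 lets the investigator stop treatment for abnormal liver tests. Section 10.2.1 requires follow-up of every Table 16-1 event, with discontinuation where appropriate. Neither document defines 'isolated'.

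**The concern.** These are mandatory stopping rules for patient safety, and section 4.5 lists transaminase elevation in siponimod's risk profile. A stopping table should never mandate less as the liver picture worsens. Here, adding raised ALT/AST and raised ALP to the same bilirubin value appears to move the patient out of a row that compels a stop and into rows that do not, or that compel it much later. The cause is one undefined word that appears in the action table but not in the event table.

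The two Hy's Law definitions are a separate, smaller matter. Exclusion 16 admits patients whose bilirubin is raised because of Gilbert's syndrome, so an eligible patient can meet one definition and not the other.

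**Working it through.** The plan states no figure on this point, so there is nothing to reproduce. The check applies each Table 16-2 row to test patients.

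**Step 1. Ordinary reading: 'isolated' means that no other liver test is raised.** All three patients have INR at most 1.5, no listed symptoms, no jaundice and no known Gilbert syndrome.

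| Table 16-2 row | ALT 4×, ALP 2.5×, TBL 2.5× | ALT 7×, ALP 2.5×, TBL 2.5× | TBL 2.5× alone |
|---|---|---|---|
| Potential Hy's Law (needs ALP not above 2×) | no | no | no |
| ALT/AST >8×; >3× with INR >1.5; >3× with symptoms; jaundice | no | no | no |
| ALT/AST >5 to ≤8× | no | repeat in 48 h; stop only after >2 weeks | no |
| ALT/AST >3 to ≤5× | repeat in a week; observe; no stop | no | no |
| ALP (isolated) | no | no | no |
| TBL (isolated) | no | no | repeat in 48 h; stop at once if it persists |

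Both combined patterns get a weaker mandated action than bilirubin alone. The liver-toxicity adverse-event row may also apply to them, but it is discretionary.

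**Step 2. Alternative reading: all matching rows apply together.** The TBL row then catches both combined patients. They get a repeat within 48 hours and a stop if the rise persists, the same as bilirubin alone, and the inversion disappears.

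**Step 3. Delay in the >5 to ≤8×ULN band, ordinary reading.** Let t be the turnaround of the bilirubin repeat. The documents do not give it; 0 to 3 days is assumed. Dosing is once daily (section 6.1.1), so days equal doses.

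- Bilirubin alone: repeat by day 2, stop at day 2 + t.
- ALT/AST row, 2-week clock from the first test: stop after day 14. Gap = 14 − 2 − t, which is 12 days at t = 0 and 9 days at t = 3.
- ALT/AST row, clock from the 48-hour repeat: stop after day 16. Gap = 16 − 2 − t, which is 14 to 11 days.

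The smallest gap is 9. There is no upper limit, for two reasons. The rise must last more than 2 weeks, and follow-up frequency in that row is left to the investigator, so the test that shows persistence may come later. A bilirubin repeat done before 48 hours also widens the gap. In the >3 to ≤5×ULN band there is no mandated stop to compare with.

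**Step 4. Limits.** With ALT 9×, INR 1.6 or jaundice, the same patient must stop immediately. So must a patient with ALT 4×, TBL 2.5× and normal ALP, as potential Hy's Law (by Table 16-1, only if the bilirubin is mainly conjugated).

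**Step 5. Hy's Law definitions.** Take a patient with known Gilbert syndrome, mainly unconjugated TBL above 2×ULN, ALT/AST above 3 and up to 8×ULN, normal ALP, INR at most 1.5, and no listed symptoms or jaundice. Under footnote a the drug stops immediately. By Table 16-1 this is not a Hy's Law case, the TBL row excludes known Gilbert syndrome, and the mandated action is the ALT/AST row alone.

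**The case against.** The strongest defence is that 'isolated' was never meant to remove combined cases. The ALT/AST block mixes single-test bands with composites (INR, symptoms), and 'isolated' may only mark the ALP and TBL blocks as having none. Or it may mean 'not a potential Hy's Law case'. Table 16-1 omits the word, which also favours applying the TBL row. On either meaning there is no gap. This stands as a possible reading, but the table does not state it. The second meaning would also be empty in the heading ALP (isolated), because potential Hy's Law already excludes ALP above 2×ULN.

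Discretion is the next defence, and it limits the point. A reader might infer that the combined patient has no route to stopping except the ALT/AST row, or goes unmonitored. The documents do not support that: section 9.1.1, section 10.2.1 and the liver-toxicity adverse-event row all allow the drug to be stopped, and follow-up is required. None of them, however, restores the mandated stop that applies to bilirubin alone.

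On Hy's Law, a reader might infer that the mismatch leaves someone under-protected. Footnote a is attached to the action row and is the broader definition, so nobody managed by Table 16-2 loses protection. Section 10.2.1 refers both to Appendix 2 for complete definitions and to Table 16-1, so it does not settle which definition governs.

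**Conclusion.** The point holds, conditional on the ordinary reading of 'isolated'. It is confined to patients without known Gilbert syndrome, listed symptoms or jaundice, with INR at most 1.5, ALT/AST above 3 and up to 8×ULN, and both ALP and TBL above 2×ULN. For them, stopping becomes discretionary up to 5×ULN. Above that, the mandated stop comes roughly 9 or more daily doses later than for bilirubin alone. The 9 rests on the assumed turnaround of at most 3 days; a slower laboratory would lower it. A reader might take 14 doses, the largest value in the arithmetic, as a ceiling. It is not one, because the plan sets no latest date for showing persistence.

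Few patients are likely affected. Section 1.1 reports transaminases above 3×ULN in 4.3% of phase II patients at higher doses, but the documents give no rate for this combination. The primary analysis is unaffected.

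The Hy's Law mismatch is an inconsistency to harmonise. The clarification should be made because the rule is a mandatory safety stop and the edits are small.

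**What to change.** 1. In Table 16-2, delete 'isolated' from the TBL heading, so that the row for TBL above 2×ULN applies whatever ALT/AST and ALP are. The Gilbert exception in that row stays, so the edit does not extend the row to every bilirubin rise. Changing the ALP heading is optional, since that row has no stopping rule.
2. Add one sentence: when several rows apply, the strictest governs. Hy's Law cases, listed symptoms, raised INR, ALT/AST above 8×ULN and jaundice then keep their immediate stop. The two combined patients in the table above would get the same action as bilirubin alone.
3. Use one potential Hy's Law definition in Table 16-1 and footnote a. Until the sponsor's clinical team decides otherwise, let footnote a govern the stopping action. If the conjugated-fraction condition is kept, it can be applied, because direct and indirect bilirubin are already in the chemistry panel (Table 8-4).

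The cost is three wording edits in Appendix 2. Section 14.1 requires a written amendment with IRB/IEC approval, so they can go into one. No new test, visit or blood draw is needed.

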16.3 Appendix 3: Specific Renal Alert Criteria and Actions and Event Follow-up

Guidance on monitoring patients with elevated blood pressure: Patients who have at least two out of the three sitting readings of blood pressure (systolic BP \geq 140 and/or diastolic BP \geq 90 mmHg) should be followed up in one month by an unscheduled visit if the scheduled visit is not due. Should systolic BP \geq 140 and/or diastolic BP \geq 90 mmHg values will be confirmed in two sitting readings out of three in the second visit, the patient should be referred to his primary care physician, an independent internist or to the specialty hypertension clinic for evaluation, diagnosis and treatment of hypertension. A standard referral letter provided by Novartis should explain a reason for referral and the information about the investigational drug (BAF312).

Patients with BP values of >180/110 mmHg on any visit during the study should be immediately referred to evaluation, diagnosis and treatment of hypertension.

The study drug should not be discontinued, unless the physician has a reason to do so.

A newly diagnosed hypertension as well as an aggravation of a preexisting condition must be reported as an AE.

Guidance on monitoring of patients with notable lymphopenia: The absolute total WBC, neutrophil and lymphocyte counts will be measured at each visit by the central laboratory. If

Amended Protocol Version No. 05 (clean)

the circulating lymphocyte level drops to $<0.2 \text{ x} 10^9/\text{L}$ when the patient is receiving the minimum study drug dose allowed in the study protocol, the lymphocyte count should be repeated in one week by the central lab to confirm the reading. If the repeat test confirms the lymphocyte count is below $0.2 \text{x} 10^9/\text{L}$ or 200 cells/mm^3 , the study drug must be interrupted and the lymphocytes count needs to be monitored weekly until the level returns to $0.2 \text{ x} 10^9/\text{L}$, then monthly until the level reaches $0.6 \text{x} 10^9/\text{L}$ values. The patient should be continuously evaluated and monitored for infections.

Re-initiation of the study drug can only be considered once the lymphocyte counts increase above $0.6x10^9/L$.

Guidance on monitoring of patients with symptoms of neurological deterioration inconsistent with MS course: Should a patient develop any unexpected neurological or psychiatric symptom/signs in the opinion of investigator (e.g. cognitive deficit, behavioral changes, cortical visual disturbances or any other neurological cortical symptoms/signs any symptom/sign suggestive of an increase of intracranial pressure) or accelerated neurological deterioration, the investigator should schedule a complete physical and neurological examination as soon as possible before beginning any treatment.

Guidance on monitoring of patients with infections: All infections that develop during the study will be reported as AEs on the respective AE eCRF pages. Treatment and additional evaluations will be performed at discretion of the investigator.

The investigator should remind the patient of the risk of infections and instruct them to promptly report any symptoms of infections to the investigator. The patients must also be reminded to always carry their Patient Information Card (with site contact information and which identifies them as participants in a clinical study with an investigational agent with potential immunosuppressive effects) and to show this to any local healthcare provider they may consult and ask that the Primary Treating Physician be contacted.

In the case of suspected or confirmed serious or atypical infection, BAF312 treatment interruption should be considered. The investigator should inform the Novartis Medical Advisor of any such cases. The elimination half-life of approximately 30 hours allows washout of the compound within a week.

When evaluating a patient with a suspected infection, the most sensitive tests available should be used (i.e. that directly detect the pathogen, as with PCR).

The investigator should consider early treatment with specific antimicrobial therapy on the basis of clinical diagnosis or suspicion thereof (e.g. antiviral treatment for herpes simplex or zoster) in consultation with infectious disease experts, as appropriate. The investigator should inform the Novartis Medical Advisor of any such cases.

Investigators should consider the added immunosuppressive effects of corticosteroid therapy for treatment of MS attack/relapse and increase vigilance regarding infections during such therapy and in the weeks following administration.

